1 INTRODUCTION

1.1 Background

Miconazole is an imidazole antifungal agent that has been available by prescription and over the counter (OTC), in different formulations, for many years. It is commonly used for different types of fungal skin infections, such as *Candida*, ringworm, jock itch, athlete's foot, nail fungus, vaginal yeast infections, and oropharyngeal candidiasis. Formulations containing up to 4% miconazole nitrate have been approved for OTC use as topical antifungal agents in cream, ointment, powder, or gel dosage forms. The 2% formulation is commonly used for dermatophytic infections.

While antifungal agents including miconazole are used in practice for the treatment of fungal otitis externa (also called otomycosis), there are currently no treatments approved by the United States (US) Food and Drug Administration (FDA) for this indication in humans. Miconazole is currently FDA-approved as a component of two veterinary combination products (Surolan and Easotic) administered otically to dogs for the treatment of canine otitis externa caused by susceptible strains of yeast and bacteria. Each veterinary product contains miconazole in combination with an antibacterial agent and a corticosteroid. The concentration of miconazole present in Surolan (23 mg/mL miconazole nitrate) is similar to the 2% concentration of miconazole planned for use in humans in this study. The concentration of miconazole present in Easotic is 15.1 mg/mL miconazole nitrate, which equates to approximately 1.5% miconazole. While the causative organism of canine otitis externa, *Malassezia pachydermatis*, is not typically associated with human otomycosis in the US, it is expected that human otomycosis, which is most commonly associated with organisms from the *Candida* and *Aspergillus* genera, would respond to concentrations of miconazole similar to those used in dogs.

The mechanisms of action of miconazole when used topically for the treatment of fungal infections involve its actions against the fungal organisms, rather than their human host. Miconazole targets the cytochrome P450-dependent enzyme 14- α -sterol demethylase, an enzyme that is also involved in mammalian cholesterol synthesis, resulting in inhibition of ergosterol biosynthesis in the cell membrane. Because ergosterol is an important component of the cell membrane, inhibition of its synthesis inhibits fungal cell growth [Vandenbosch 2012]. In addition to its activity toward the enzyme 14- α -sterol demethylase, miconazole also leads to increased reactive oxygen species in fungal organisms, which appears to result in fungicidal activity [Vandenbosch 2010; Musaji 2010].

The mechanisms of action of miconazole against fungi in general appear to be applicable to fungi associated with otomycosis. Data from a recently-completed Phase 2 study of the investigational product (2% miconazole oil; Hill Dermaceuticals, Inc. Study HD-MCZ-PHII-DRF062016) demonstrated 25.0% of subjects with therapeutic cure, defined as a negative fungal culture plus the absence of each of the otomycosis signs and symptoms of pruritus, debris, fungal elements, and pain, compared with 7.1% of subjects treated with control product (vehicle oil), at the final test of cure study visit, following a 14-day treatment regimen. The percentage of subjects with therapeutic cure following a 7-day treatment regimen was 8.3%, supporting the 14-day treatment duration for miconazole.

Clinical studies of 2% miconazole conducted outside of the United States also suggest the efficacy of miconazole in the treatment of human otomycosis [Kiakojuri 2007; Vennewald 2010; Navaneethan 2015]. *In vitro* studies of miconazole have also demonstrated activity of miconazole against some clinical isolates of fungi associated with human otomycosis in the US [Bassiouny 1986; Stern 1988].

Adverse event (AE) data from the recently-completed Phase 2 study of the investigational study support the acceptable safety of miconazole oil and generally demonstrated a lower percentage of patients with treatment-emergent AEs (TEAEs) in each of the miconazole oil groups (which were treated for either 7 or 14 days) compared with the vehicle oil group (which was treated for 14 days). The most frequently reported TEAEs in the 14-day miconazole oil group in the Phase 2 study were application site pruritus, application site pain, and ear infection fungal (Table 1). In each case except for ear infection fungal, a higher percentage of subjects in the 14-day vehicle oil group compared with the 14-day miconazole oil group reported the TEAE. Similar results were observed for the 7-day miconazole oil group, although a higher percentage of subjects in the 7-day miconazole oil group had the TEAE of application site infection compared with the 14-day miconazole oil and 14-day vehicle oil groups.

Table 1 Treatment-emergent Adverse Event Preferred Terms Reported in >1 Patient in the Safety Population of Hill Dermaceuticals, Inc. Study HD-MCZ-PHII-DRF062016

System Organ Class Preferred Term	Study Group		
	7-Day Miconazole Oil (N=23) n (%)	14-Day Miconazole Oil (N=22) n (%)	14-Day Vehicle Oil (N=20) n (%)
Ear and labyrinth disorders	0 (0.0)	0 (0.0)	4 (20.0)
Ear pain	0 (0.0)	0 (0.0)	2 (10.0)
Tympanic membrane perforation	0 (0.0)	0 (0.0)	2 (10.0)
General disorders and administration site conditions	4 (17.4)	6 (27.3)	9 (45.0)
Application site pain	1 (4.3)	2 (9.1)	5 (25.0)
Application site pruritus	3 (13.0)	4 (18.2)	6 (30.0)
Infections and infestations	4 (17.4)	3 (13.6)	2 (10.0)
Application site infection	2 (8.7)	0 (0.0)	0 (0.0)
Ear infection fungal	1 (4.3)	2 (9.1)	1 (5.0)

Source: Study HD-MCZ-PHII-DRF062016 Clinical Study Report Table 18

No serious AEs (SAEs) were reported in the Phase 2 study. AEs leading to discontinuation in the Phase 2 study were observed in a higher percentage of subjects in the 14-day vehicle oil group compared with either the 14-day miconazole oil or 7-day miconazole oil group, providing further evidence of an acceptable safety profile for miconazole oil (Table 2).

Table 2 Treatment-emergent Adverse Event Leading to Permanent Withdrawal of Study Drug and/or Early Discontinuation from the Study in the Safety Population of Hill Dermaceuticals, Inc. Study HD-MCZ-PHII-DRF062016

Preferred Term	Study Group		
	7-Day Miconazole Oil (N=23) n (%)	14-Day Miconazole Oil (N=22) n (%)	14-Day Vehicle Oil (N=20) n (%)
Application site discharge	0 (0.0)	0 (0.0)	1 (5.0)
Application site erosion	0 (0.0)	1 (4.5)	0 (0.0)
Application site infection	1 (4.3)	0 (0.0)	0 (0.0)
Application site pain	0 (0.0)	1 (4.5)	3 (15.0)
Application site pruritus	1 (4.3)	1 (4.5)	1 (5.0)
Dysgeusia	0 (0.0)	1 (4.5)	0 (0.0)
Ear pain	0 (0.0)	0 (0.0)	1 (5.0)
Nausea	0 (0.0)	0 (0.0)	1 (5.0)
Tympanic membrane perforation	0 (0.0)	0 (0.0)	2 (10.0)

Source: Study HD-MCZ-PHII-DRF062016 Clinical Study Report Table 19

1.2 Study Purpose

The purpose of this study is to gather confirmatory data on the efficacy and safety of 2% miconazole oil after topical otic administration in subjects with otomycosis. During the Randomization Period of the Enrollment A portion of the study, a 14-day regimen of twice-daily administration of 2% miconazole oil will be compared with the same treatment regimen using the product vehicle. During the Optional Open-label Extension of the Enrollment A portion and the Enrollment B portion of the study, a 14-day regimen of twice-daily administration of 2% miconazole oil will be administered in an open-label fashion in order to gather safety information in additional subjects.

1.3 Inclusion of Subjects with Peanut Allergy

Miconazole oil contains refined peanut oil. Inclusion in this study of subjects with peanut allergy is justified by studies and publications documenting safe use of the refined peanut oil, as well as products containing the refined peanut oil (such as DermOtic, which is the same product as the Derma-Smoothe/FS for which two safety studies were performed in subjects with known hypersensitivity to peanuts) [Yunginger 2001; Paller 2003]. Reports also exist of subjects with known peanut allergy who have continued to safely use products such as Derma-Smoothe/FS even after an anaphylactic reaction to peanuts [Paller 2003]. The refined peanut oil used in the Derma-Smoothe/FS, DermOtic, and miconazole oil products has been treated to remove the peanut proteins which are generally responsible for allergic reactions to peanuts. Thus, the inclusion of subjects with peanut allergy in this study is not expected to pose an excessive risk to these subjects.

1.4 Compliance with Good Clinical Practice

The investigator and all study staff will conduct the study in compliance with this protocol and FDA regulations, all applicable federal, state, and local laws, rules and regulations relating to the conduct of a clinical study, the ethical principles of the Declaration of Helsinki, and the current International Conference on Harmonisation (ICH) Good Clinical Practice (GCP) guidelines.

2 STUDY OBJECTIVES

[figure not shown]
The objectives of the study are to:

- Confirm the efficacy of miconazole oil compared with vehicle over a 14-day treatment duration in subjects with otomycosis
- Assess the safety of miconazole oil over a 14-day treatment duration

3 STUDY DESIGN

This study will be conducted in 2 portions (see also Figure 1 for a schematic diagram of the study design):

1. Enrollment A, which will consist of 2 treatment periods as follows and will be conducted in subjects with otomycosis:
 - a. A randomized, double-blind, parallel-group treatment period. This treatment period will be referred to as the "Randomization Period" and will be followed by:
 - b. An optional, open-label treatment period with miconazole oil. This treatment period will be referred to as the "Optional Open-label Extension."
2. Enrollment B, which will consist of open-label treatment with miconazole oil in subjects who will not be required to have signs and symptoms of otomycosis.

Figure 1: Diagram of Study Design

- Subjects must meet all eligibility criteria in Section 4.1 to be randomized in Enrollment A.
- Subject must have a visual presence of fungal elements to be enrolled in the Optional Open-label Extension.
- Subject must meet all eligibility criteria in Section 4.2 to receive treatment with miconazole oil in Enrollment B.

3.1 Enrollment A

The study will start with Enrollment A, in which an estimated 220 male or female subjects with otomycosis will receive study drug, although this number may be higher or lower depending on the percentage of subjects eligible to be included in the modified intent-to-treat (MITT) population (see Section 10.4.2). Subjects will be randomly assigned in a 1:1 ratio to receive miconazole oil or vehicle, for 14 days. The study drug will be administered as 5 drops per ear at ~30 mg per drop instilled into the external ear canal of the ear(s) affected by otomycosis.

3.1.1 Randomization Period

During the Randomization Period, both the subject and the investigator and study staff will be blinded as to the contents of the study drug.

At Screening/Baseline (Day 1), potentially eligible subjects will provide informed consent, and subjects will undergo screening evaluations to include a physical examination, an assessment of the signs and symptoms of otomycosis (pruritus, debris, visual examination for presence of fungal elements, and aural fullness), and an evaluation of medical history. Urine will be obtained for pregnancy screening in female subjects of childbearing potential. Prior and concomitant medications will be reported. Subjects with positive signs and symptoms of otomycosis and who meet all other eligibility criteria will be entered into the study. A fungal culture of the affected ear(s) will be taken, then debris will be cleaned from the affected ear(s) following the site's normal procedures. The subject will be randomized, and study drug will be weighed and dispensed to the subject along with a subject diary. The subject will then begin treatment with study drug. The subject or caregiver will instill the first dose of study drug at the site, under the supervision of the investigator or site personnel. Adverse events (AEs) will then be assessed. The subject will then leave the clinic and continue to administer the study drug and to complete the subject diary twice per day as instructed. Subjects will be instructed to avoid getting water in the ear, to consider drying excessive water in the ear by using a blow dryer, and to place a Vaseline-impregnated cotton ball over the affected ear(s) to help keep water out of the ear while bathing or showering.

Subjects will return to the clinic on Day 8 for the On Treatment Visit, at which time a clinical evaluation of the signs and symptoms of otomycosis, a cleaning of the affected ear(s) (following the site's normal procedures), a review of the subject diary, and an assessment of AEs and concomitant medications will be performed. Subjects will continue to administer the study drug and to complete the subject diary twice per day, up through Day 14, following the same instructions as provided at the Screening/Baseline Visit on Day 1.

Subjects will return to the clinic on Day 15 for the End of Treatment Visit, at which time a clinical evaluation of the signs and symptoms of otomycosis and a fungal culture of the affected ear(s) will be performed; however, a fungal culture will not be required at this visit for subjects known to have a negative fungal culture at Screening/Baseline, as assessed after at least 14 days of incubation by the clinical laboratory performing the fungal culture. AEs and concomitant medications will also be assessed, and the subject will return all unused study drug along with the completed subject diary.

Subjects will return to the clinic on Day 22 for the Test of Cure Visit, at which time an assessment of clinical signs and symptoms of otomycosis and a fungal culture of the affected ear(s) will be performed; however, a fungal culture will not be required at this visit for subjects known to have a negative fungal culture at Screening/Baseline, as assessed after at least 14 days of incubation by the clinical laboratory performing the fungal culture. AEs and concomitant medications will also be assessed. A urine pregnancy test will be performed in women of childbearing potential.

Efficacy assessments will include fungal culture of the affected ear(s), and assessments of clinical signs and symptoms of otomycosis. In cases of bilateral otomycosis, both ears will be treated and evaluated by the investigator, but only 1 ear will be used as the study ear for efficacy analyses, the designation of which will be performed at the end of the study in accordance with the following. If only 1 ear has a positive fungal culture at Screening/Baseline, that ear will be used as the study ear for efficacy analyses. If both ears have a positive fungal culture at Screening/Baseline, the ear with the worse infection at Screening/Baseline, as assessed by the investigator by taking into account the clinical signs and symptoms of otomycosis, will be used as the study ear for efficacy analyses. If both ears have a positive fungal culture and are determined by the investigator to have the same degree of infection at Screening/Baseline, the left ear will be used as the study ear for the purposes of efficacy analyses.

Safety assessments will include AEs.

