4 STUDY SUBJECTS

4.1 Enrollment A

4.1.1 Inclusion Criteria

In order to be eligible for Enrollment A, subjects must meet all of the following criteria:

1. Male or non-pregnant, non-lactating females
2. Diagnosis of uncomplicated otomycosis of the external ear only, in the ear(s) that will be treated with study drug, with a score for fungal elements of >0 in each ear to be treated with study drug (see Section 7.4 for definitions of the scores for each of the otomycosis signs and symptoms). Subjects must also have at least two of the following signs or symptoms of otomycosis in each ear to be treated with study drug: pruritus, >1; debris, >1; or aural fullness, >0
3. General good health as determined by medical examination and medical history, and who are free of clinically significant disease, including diabetes mellitus that is not well-controlled or that could interfere with the study

4. Females of childbearing potential must have had a negative urine pregnancy test at Screening/Baseline and must agree to use an effective method of contraception (as defined in Section 8.5) from Screening/Baseline up through the Test of Cure Visit (see Section 6). Females of childbearing potential include any female who has experienced menarche and who has not undergone successful surgical sterilization (hysterectomy, bilateral tubal ligation or bilateral oophorectomy) or is not postmenopausal (defined as amenorrhea >12 consecutive months). Females who are using oral, implanted, or injectable contraceptive hormones, an intrauterine device (IUD), barrier methods (diaphragm, condoms, spermicide) to prevent pregnancy, practicing abstinence or where partner is sterile (e.g., vasectomy), should be considered to be of childbearing potential
5. Subjects and/or their caregivers (as appropriate for the age of the subject) must have full legal capacity to volunteer
6. Subjects and/or their caregivers must have completed an appropriately administered institutional review board (IRB)-approved informed consent and assent (as applicable) prior to any study related procedures
7. Subjects and their caregivers (as applicable) must agree to comply with all requirements of the protocol

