8. For subjects with only one ear meeting all study eligibility criteria, the subject will be eligible for the study, and the ear meeting all eligibility criteria will be treated with study drug and considered to be the study ear for the purposes of study evaluations. In case of bilateral otomycosis in which both ears meet all study eligibility criteria, the subject will be eligible for the study, both ears may be treated with study drug, and the worse ear will be considered to be the study ear for the purposes of study evaluations. If both ears meet study eligibility criteria and are determined by the investigator to have the same degree of infection at Screening/Baseline, the left ear will be considered to be the study ear for the purposes of study evaluations.

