4.1.2 Exclusion Criteria

Subjects meeting any of the following criteria will not be eligible for Enrollment A:

1. Any other dermatoses or conditions of the ear that may interfere with the evaluation of otomycosis or with safety evaluations, including concomitant otic infections (including bacterial infection) other than otomycosis that require antimicrobial treatment, disease that has spread beyond the external ear(s), or pre-existing skin atrophy of the affected ear(s) that will be treated with study drug
2. Tympanostomy tube or perforated tympanic membrane in the ear(s) that will be treated with study drug
3. History of prior surgery directly affecting and compromising the external auditory canal and/or tympanic membrane of the ear(s) that will be treated with study drug, except for prior tympanostomy tube(s) that have already been removed and completely healed
4. Use, in the ear(s) that will be treated with study drug, of any topical medicated treatments for otomycosis within 14 days of study entry:

- Topical corticosteroids prescribed specifically for the treatment of otomycosis are prohibited to be used within 14 days of study entry; however, use of topical corticosteroids for any other reason (e.g., for bacterial otitis externa and/or for control of symptoms in the ear such as itching and/or pain) will not require a 14-day washout
 - Alcohol and/or peroxide are prohibited when prescribed/used by a health care provider specifically for the treatment of otomycosis within 14 days of study entry; however, use of these substances for other purposes (e.g., as a drying agent) will not require a 14-day washout
 - Use of boric acid for any reason is prohibited within 14 days of study entry
5. Use of any systemic antifungal therapy within 28 days of study entry, warfarin within 28 days of study entry, immunosuppressive or immune-stimulating drugs within 28 days of study entry, or systemic steroids within 3 months of study entry
 6. Fever of $\geq 100^{\circ}\text{F}$ at study entry
 7. Otomycosis that has been unresponsive to previous antifungal treatment
 8. Known hypersensitivity to any of the components in the test formulation
 9. Participation in another investigative trial within 28 days of study entry
 10. Participation in the sponsor's previous miconazole oil Study HD-MCZ-PHII-DRF062016 unless the subject was enrolled into either the vehicle or the 7-day miconazole oil group of that study.

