7.5 Fungal Culture

At designated visits, the investigator or designee will obtain a sample from the external ear to be sent to a central laboratory for fungal culture. Techniques for obtaining and handling the sample and sending it to the laboratory will be described in a separate laboratory manual. If both ears will be treated with study drug, both ears will be cultured.

The central laboratory will grow and identify fungal organisms from the sample provided by the investigator. The central laboratory will also test the susceptibility of the fungal isolates to miconazole.

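### In Enrollment A, Section 3.1.1 and inclusion criterion 8 give different rules for which ears are treated, and which ear is analysed, when both ears have otomycosis

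*Combined protocol and SAP*

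**What the plan says.** Four places bear on a randomized subject with otomycosis in both ears.

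- Section 3.1.1: "In cases of bilateral otomycosis, both ears will be treated and evaluated by the investigator". No condition is placed on the second ear. Section 3.1 likewise has drug "instilled into the external ear canal of the ear(s) affected by otomycosis".
- Section 4.1.1, criterion 8, two eligible ears: "In case of bilateral otomycosis in which both ears meet all study eligibility criteria", the subject may enter and "both ears may be treated with study drug, and the worse ear will be considered to be the study ear".
- Section 4.1.1, criterion 8, one eligible ear: "the ear meeting all eligibility criteria will be treated with study drug and considered to be the study ear".
- Section 7.5: "If both ears will be treated with study drug, both ears will be cultured". It does not address an affected ear that will not be treated. The baseline culture described in 3.1.1 is of the affected ear or ears.

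Eligibility is set ear by ear. Inclusion criterion 2 requires otomycosis "with a score for fungal elements of >0 in each ear to be treated with study drug", plus other score thresholds, and exclusion 2 reads "Tympanostomy tube or perforated tympanic membrane in the ear(s) that will be treated with study drug". A subject can therefore have disease in both ears and only one eligible ear.

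For the analysis, 3.1.1 and 10.5.1 first take the culture-positive ear if only one is positive, then the clinically worse ear, then the left. The synopsis has the investigator weigh symptoms and culture together.

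**The concern.** Two sites could each follow a section of the protocol and treat the same bilateral subject differently: one ear or two. A subject with one ineligible affected ear might be enrolled at one site and excluded at another.

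The second issue is the primary endpoint. Criterion 8 ties the study ear to eligibility and severity, while 10.5.1 ties it to baseline culture and does not ask whether the ear was assigned to treatment. If those choices diverge, the ear scored for therapeutic cure may be one that was never meant to receive randomized drug.

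**Working it through.** **1. Planned sample size.** Inputs from Section 10.3: 25.0% versus 7.1%, two-sided 0.05, 80% power, chi-square. With pooled variance and no continuity correction, the mean rate is (0.25 + 0.071)/2 = 0.1605, and

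n per group = [1.960 × √(2 × 0.1605 × 0.8395) + 0.842 × √(0.25 × 0.75 + 0.071 × 0.929)]² / 0.179² ≈ 64.8, so 65.

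That is 130 in total against the stated 128, a match within 3%. Power at 64 per group is 79.5%. The analysis uses one ear per subject, so the number of ears treated does not enter this calculation.

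**2. The treatment rules side by side.**

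| Subject with disease in both ears | Section 3.1.1 | Criterion 8 |
|---|---|---|
| Both ears eligible | Both treated (*will*) | Both may be treated (*may*) |
| One ear eligible | Both treated, read literally | The eligible ear treated |

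Section 9.1.1 gives the order of instillation if both ears are being treated, but not when both should be. It settles neither row. Reading 3.1.1 as assuming two eligible ears removes the second-row conflict but leaves the first.

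**3. Exposure.** Inputs: 5 drops of about 30 mg per ear (3.1), 2% miconazole, twice daily for 14 days (1.2).

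- Per ear per application: 5 × 30 mg = 150 mg product.
- Applications: 2 × 14 = 28.
- One ear: 28 × 150 mg = 4.2 g product; × 0.02 = 84 mg miconazole.
- Two ears: 8.4 g product; 168 mg miconazole.

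Total exposure differs twofold. The dose per ear is the same on either reading.

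**4. How an untreated ear can become the study ear.**

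1. Under criterion 8, one of two affected ears goes untreated.
2. Both are cultured at baseline, because 3.1.1 cultures affected ears. Section 7.5 does not forbid this.
3. Only the untreated ear grows fungus. The MITT definition (10.4.2) is met at subject level.
4. Section 10.5.1 names that ear as the study ear. Criterion 8 names the other ear if only one was eligible. If both were eligible, it names the worse ear, or the left if they are equal.
5. Sections 7.4.1 to 7.4.4 score pruritus, debris, fungal elements and aural fullness only for ears under treatment, so no scores are required for the study ear.
6. Therapeutic cure and clinical cure are then missing and are imputed as failure (10.5.4), whichever arm the subject is in.

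Such a subject also cannot meet the per-protocol compliance range, which counts applications in the study ear (10.4.3).

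**The case against.** The strongest reply is that the texts can be read together. Criterion 8 is an eligibility statement that permits bilateral treatment, and 3.1.1 is the conduct text that directs it. A site that treats both eligible ears complies with both. That is correct, so the conflict does not bite in every bilateral case. But a site that treats one of two eligible ears complies with criterion 8 and breaches 3.1.1, and nothing says which governs.

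A reader might infer that 3.1.1 would put drug into an ear with a tube or perforated membrane. The documents do not support this. The ear-level exclusions attach to ears that will be treated. If 3.1.1 makes the second ear one of those, the subject fails eligibility; if criterion 8 governs, that ear is not treated. What changes is enrolment, not dosing of an excluded ear.

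It can also be said that the untreated study ear mixes incompatible rules. Within 3.1.1 the designation rule presumes both ears are treated, criterion 8 names the treated ear when only one is eligible, and symptom scoring and per-protocol compliance presume a treated study ear. This narrows the problem to Section 10.5.1, which governs the efficacy analysis and does not carry the premise over.

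**Conclusion.** The inconsistency is in the current protocol text and should be corrected. It affects how many ears are treated (about 4.2 g versus 8.4 g of product in total), possibly the eligibility of a subject with one ineligible affected ear, and which ear is analysed. The untreated-study-ear result needs three things together: one of two affected ears untreated, both cultured, and only the untreated one positive.

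The number of subjects cannot be derived, because the documents give no bilateral share. A reader might assume 5% to 20% of 220, or 11 to 44 subjects. That would count every bilateral subject, not those treated or analysed differently, and the share is only an assumption. A reader might also infer material dilution of the treatment effect. The mechanism is real, since failure is imputed in both arms, but its size is unknown. For scale, one miconazole subject switched from cure to failure lowers that arm's rate by 1/64 = 1.6 percentage points. Sample size and power as planned are unaffected.

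**What to change.** Reconcile the synopsis, 3.1, 3.1.1, criterion 8 and 7.5 so that one rule states which ears are treated and which are cultured in bilateral disease, both when two ears are eligible and when one is. No view is taken here on which treatment rule is right.

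In 3.1.1, criterion 8 and 10.5.1, with the synopsis brought into line, use one study-ear rule limited to ears designated for study treatment before randomization. The limit should not be to ears actually dosed. That would add a post-randomization condition and leave a randomized, culture-positive, never-dosed subject without a study ear, although 10.4.2 keeps that subject in the MITT and 10.5.4 scores the outcome as failure. With designation fixed beforehand, MITT membership and failure imputation stay as planned.

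If the reconciled culture rule still covers affected ears that are not designated, add a sentence on how a subject whose only positive culture comes from such an ear is scored.

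The cost is wording in a protocol amendment and the matching analysis text. No visits, procedures or subjects are added.
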